6.1 Demographics and Baseline Characteristics

Demographic and baseline characteristics information will be collected at the Baseline visit of the study and will be summarized for the FAS. The number of observations, mean, standard deviation, median, minimum and maximum will be summarized for continuous variables. Categorical or discrete variables will be summarized via frequencies and percentages. Summary statistics will be computed for each treatment group and overall.

Main Demographic and Baseline Characteristics

- Sex (male, female)
- Age (years)
- Age Categories ($<65, \ge 65 75, \ge 75$ years)
- Race (White, Black or African American, American Indian or Alaska Native, Native Hawaiian or Other Pacific Islander, Asian, Other)

b. Week 16 x-rays will be performed for all subjects who met the protocol specified rescue criteria at Week 16 (i.e., not achieving at least 20% improvement in either or both TJC68 and SJC66 at both Week 12 and Week 16).

c. Not protocol specified visit for x-ray assessment, but will be used to capture unscheduled or PD x-rays.

- Geographic Region (North America, Western Europe and Oceania, Eastern Europe, Latin-America, Asia, and Other)
- Ethnicity (Hispanic or Latino, Not Hispanic or Latino)
- Weight (kg)
- Height (cm)
- Body Mass Index (BMI) (kg/m²)
- Body Mass Index (BMI) Category (kg/m²) (BMI \leq 25, BMI \geq 25)

PsA Medical History, Prior and Baseline Treatments

- Duration of PsA symptoms in years
- Duration of PsA diagnosis in years
- Rheumatoid Factor (RF) status: Positive or Negative
- Anti-CCP status: Positive or Negative
- Number of prior non-biologic DMARDs $(0, 1, 2, \ge 3)$
- Current use of at least 1 non-biologic DMARD at baseline (Yes or No)
- Concomitant non-biologic DMARD at baseline (MTX alone, MTX and other non-biologic DMARD, non-biologic DMARD other than MTX)
- Current NSAID use at baseline (Yes or No)
- Current Corticosteroid use at baseline (Yes or No)

Baseline Disease Characteristics

- Tender joint count (TJC68) defined as the number of tender joints out of 68 assessed joints
- Swollen joint count (SJC66) defined as the number of swollen joints out of 66 assessed joints
- Physician's global assessment of Disease Activity Numeric Rating Scale (0 - 10 NRS)
- Patient's assessment of pain (0 10 NRS)
- Patient's global assessment of disease activity (0 10 NRS)

- Health Assessment Questionnaire Disability Index (HAQ-DI)
- High sensitivity C-reactive protein (hsCRP)
- Categories for hsCRP: equal or below vs. above ULN (2.87 mg/L)
- Body Surface Area (BSA) with Psoriasis (as categorical with $< 3\%, \ge 3\%$)
- Body Surface Area (BSA) with Psoriasis (as continuous for subjects with BSA-Ps > 0%)
- Static Investigator Global Assessment of Psoriasis (sIGA) (as a categorical variable)
- Psoriasis Area and Severity Index (PASI) score (for subjects with ≥ 3% Body Surface Area (BSA) psoriasis)
- Erythrocyte sedimentation rate (ESR)
- Psoriatic arthritis disease activity score (PASDAS)
- Disease Activity In Psoriatic Arthritis (DAPSA) score
- Presence of Dactylitis (LDI > 0)
- Leeds Dactylitis Index (LDI) (out of subjects with presence of dactylitis (LDI > 0))
- Total dactylitis count (out of subjects with presence of dactylitis (LDI > 0))
- Presence of enthesitis (total enthesitis count > 0)
- Total enthesitis count (out of subjects with presence of enthesitis (total enthesitis count > 0))
- Spondyloarthritis Research Consortium of Canada (SPARCC) Enthesitis Index (out of subjects with SPARCC Enthesitis Index > 0)
- Leeds Enthesitis Index (LEI) (out of subjects with LEI > 0)
- DAS28 [CRP]
- DAS28 [ESR]
- Presence of Psoriatic Spondylitis
- Ankylosing Spondylitis Disease Activity Score (ASDAS) (out of subjects with presence of psoriatic spondylitis)
- Bath AS Disease Activity Index (BASDAI) (out of subjects with presence of psoriatic spondylitis)

- Morning stiffness (mean of BASDAI Questions 5 and 6)
- Morning stiffness severity 0 10 (BASDAI Question 5)
- Morning stiffness duration 0 10 (BASDAI Question 6)
- Radiographic endpoints:
 - Presence of \geq 1 erosion
 - o Total modified PsA Sharp/van der Heijde Score (SHS) score
 - Erosion score
 - Joint space narrowing score

Patient Report Outcomes at Baseline

- Functional Assessment of Chronic Illness Therapy (FACIT)-Fatigue
- 36-Item Short Form Health Survey (SF-36) Version 2: physical component summary, mental component summary, and the 8 sub-domain scores
- EuroQol-5D-5L (EQ-5D-5L) index and VAS score
- Work Productivity and Activity Impairment (WPAI)
- Self-Assessment of Psoriasis Symptoms (SAPS)

Tobacco/Nicotine and Alcohol Use

- Tobacco/Nicotine Use [user, ex-user, non-user, unknown]
- Alcohol Use [drinker, ex-drinker, non-drinker, unknown]

6.2 Medical History

Medical history data will be summarized and presented for FAS population using System Organ Class (SOC) and Preferred Term (PT) as in the Medical Dictionary for Regulatory Activities (MedDRA) dictionary. The number and percentage of subjects with a particular PT will be summarized for each randomized treatment group as well as overall. Subjects reporting more than one PT within a SOC will be counted only once for that SOC. No statistical comparison will be performed for medical history reporting.

6.3 Prior Treatment and Concomitant Medications

Prior and concomitant medications will be summarized by each randomized treatment group as well as overall for FAS. Prior medications are those medications taken prior to the first dose of study drug. This includes medications with a start date before the first study drug administration date, regardless of the end date of these medications. Medications taken on the day of the first dose of study drug are not counted as prior medications. Concomitant medications are those medications, other than study drug, taken after the first dose of study drug and within 1 day of the last dose of study drug for the subjects on upadacitinib and placebo, and within 14 days of the last dose of study drug for the subjects on adalimumab, respectively. This includes medications with a start date between first study drug administration and last study drug administration + 1 or 14 day, as well as, medications with a start date prior to first dose of study drug and which are ongoing after first dose of study drug. Medications taken on the day of the first dose of study drug are counted as concomitant medications.

The number and percentage of subjects who received a prior medication and the number and percentage of subjects who received a concomitant medication will be tabulated separately by the generic name assigned by the most current version of the World Health Organization (WHO) Drug Dictionary.

6.4 Protocol Deviations

Protocol deviations based on ICH deviation criteria are categorized as follows:

- 1. Those who entered the study even though they did not satisfy the entry criteria
- 2. Those who developed withdrawal criteria during the study and were not withdrawn
- 3. Those who received the wrong treatment or incorrect dose, and
- 4. Those who received an excluded or prohibited concomitant medication.

The protocol deviations listed above will be summarized and listed by treatment group.

7.0 Patient Disposition

The following will be summarized by randomized treatment group as well as overall:

- number of subjects randomized,
- number of subjects included in key analysis populations (Full Analysis Set and Per Protocol Analysis Set for efficacy analysis, Safety Analysis Set for safety analysis),
- number of subjects who completed Period 1 study participation,
- number of subjects who entered Period 2,
- number of subjects who completed overall study (Period 1 and Period 2) participation (if applicable).

[figure not shown]
Premature discontinuation details will be further summarized separately for Period 1 and Period 2 as follows.

Period 1

The number and percentage of subjects completed Period 1 and prematurely discontinued in Period 1 will be summarized by randomized treatment group, separately by study drug and study participation completion/discontinuation, with the reason for discontinuation collected from CRF by the following categories:

- Adverse event (AE)
- Withdrew consent
- Lost to follow-up
- Lack of efficacy
- Other.

In addition, the number and percentage of subjects who entered Period 2 will also be summarized by randomized treatment group.

For Week 24 reporting, this summary will also be presented for study drug completion/discontinuation by Week 24.

Period 2

Period 2 patient dispositions and reason for discontinuation will be summarized with the same categories as given above for Period 1 for overall total and by treatment in Period 2 defined as follows:

- 1. Upadacitinib 15 mg QD
- 2. Upadacitinib 30 mg QD
- 3. Adalimumab 40 mg EOW

Among the subjects who entered Period 2 participation (regardless of whether subject entered Period 2 on study drug), the number and percentage of subjects who completed and prematurely discontinued study participation in Period 2 will be summarized.

Among the subjects who entered Period 2 on study drug, the number and percentage of subjects who completed and prematurely discontinued study drug in Period 2 will be summarized.

Summary of Dose Switch from Upadacitinib 30 mg QD to 15 mg QD

Starting with Amendment 6.01 (for Japan) and Amendment 7 and 7.01(for global), subjects receiving upadacitinib 30 mg QD will be switched to upadacitinib 15 mg QD. The visit at which dose switch occurs could be different for each subject. For subjects on upadacitinib 30 mg QD in Period 2, the number and percentage of subjects switching to upadacitinib 15 mg QD at each visit will be summarized.

8.0 Study Drug Exposure and Compliance

8.1 Study Drug Exposure

For short term up to Week 24, the duration of exposure to study drug will be summarized for the safety analysis set by the randomized treatment groups.

For long term, the duration of exposure to study drug will be summarized for the safety analysis set by the following groups.

1. Upadacitinib 15 mg QD

This includes upadacitinib 15 mg QD exposure from subjects starting on upadacitinib 15 mg QD and subjects switching from placebo to upadacitinib 15 mg QD.

2. Upadacitinib 30 mg QD

This includes upadacitinib 30 mg QD exposure from subjects starting on upadacitinib 30 mg QD and subjects switching from placebo to upadacitinib 30 mg QD. Exposure is censored at time of dose switch from upadacitinib 30 mg QD to upadacitinib 15 mg QD.

3. Upadacitinib 15 mg QD switched from upadacitinib 30mg QD

This includes Upadacitinib 15 mg QD exposure from subjects who switched dose from upadacitinib 30 mg QD to upadacitinib 15 mg QD.

4. Adalimumab 40 mg EOW

Exposure to upadacitinib and placebo is defined as last dose date minus first dose date plus 1 day. Exposure to adalimumab is defined as last dose date minus first dose date plus 14 days.

Starting with Amendment 6.01 (for Japan) and Amendment 7 and 7.01(for global), subjects receiving upadacitinib 30 mg QD will be switched to receiving upadacitinib 15

mg QD. Exposure to upadacitinib 30 mg QD (Groups 2) will be censored prior to the day subject received the first dose of upadacitinib 15 mg QD, and subsequent exposure to upadacitinib 15 mg QD will be summarized under separate groups (Groups 3).

The duration of exposure to study drug will be summarized for each group as specified above, with the number of subjects, mean, standard deviation, median, minimum and maximum values. In addition, the number and percentage of subjects exposed to study drug will be summarized for the following cumulative duration intervals.

- ≥ 2 weeks
- ≥ 1 month
- \geq 3 months
- \geq 6 months
- ≥ 9 months
- ≥ 12 months
- ≥ 18 months
- ≥ 2 years
- ≥ 2.5 years
- ≥ 3 years
- ≥ 3.5 years
- \geq 4 years
- ≥ 4.5 years

8.2 Compliance

Study drug compliance will be summarized for each treatment group at Week 24. The summary will be performed for UPA/PBO tablets and ADA/PBO injections separately. For tablets, compliance is defined as the number of tablets taken (i.e., the difference between the number of tablets dispensed and the number of tablets returned) during the subject's participation up to Week 24 divided by the number of days that the subject was in the Treatment Phase up to Week 24. For injections, compliance is defined as the

number of ADA injections administered during the subject's participation up to Week 24 divided by the number of injections planned during the subject's participation in the Treatment Phase up to Week 24.

9.0 Efficacy Analysis

9.1 General Considerations

There are two sets of planned efficacy analysis: efficacy analysis through Week 24 and long-term efficacy analysis. Unless otherwise noted, all efficacy analyses will be carried out using the FAS population.

9.1.1 Efficacy Analysis at Different Phases of the Study

[figure not shown]
Efficacy Analysis by Week 24

Standard efficacy analysis by randomized treatment groups (upadacitinib 15 mg QD, upadacitinib 30 mg QD, adalimumab 40 mg EOW and the combined placebo groups) will be performed on efficacy data up to Week 24. No protocol-defined treatment switching will occur prior to the time point. Formal statistical inference will be generated, and results from this set of analysis will be used as the key efficacy findings of this study.

Long-Term Efficacy Analysis

Long-term efficacy analysis will be performed on As Observed data (defined in Section 9.1.2) by randomized treatment group sequence as described below:

- 1. Placebo → Upadacitinib 15 mg QD
- 2. Placebo → Upadacitinib 30 mg QD
- 3. Upadacitinib 15 mg QD
- 4. Upadacitinib 30 mg QD
- 5. Adalimumab 40 mg EOW

Descriptive statistics and 95% confidence intervals will be provided for all treatment sequences. In addition, comparisons between each upadacitinib dose and adalimumab (treatment sequences 3, 4, and 5) will be provided up to Week 56. Treatment comparisons may also be provided after Week 56 as appropriate.

For long term efficacy analysis, subjects will continue to be summarized under the treatment sequences as described above, regardless of dose switch from upadacitinib 30 mg QD to upadacitinib 15 mg QD – i.e., for treatment sequences 2 and 4, data collected after dose switch will continue to be summarized under the same treatment sequences. The visit at which dose switch occurs could be different for each subject. The first and last visits at which dose switch occurs will be noted in the summary. In addition, sensitivity analyses will be performed where the subjects who switched from upadacitinib 30 mg QD to 15 mg QD will be censored at the time of dose switch, and efficacy values before and post switch will be summarized separately.

9.1.2 Handling of Missing Data and Intercurrent Events

Non-Responder Imputation (NRI) Approach

The NRI approach will handle data for binary endpoints as follows.

- Subjects who prematurely discontinue from study drug will be considered as non-responders for all subsequent visits after discontinuation.
- In addition, any subject with any missing value for the binary endpoints at a specific visit will be treated as non-responder for that visit.

NRI data handling will be used for the primary estimand (refer to Section 9.2.1) for the binary endpoints.

Mixed-Effects Model Repeated Measures (MMRM) Up to Week 24

The repeated measure analysis will be conducted using mixed models including observed data at all visits. For the MMRM analysis, data collected after premature discontinuation

of study drug will be excluded. The mixed model includes the categorical fixed effects of treatment, visit, treatment-by-visit interaction, the stratification factor current DMARD use (yes/no) and the continuous fixed covariates of baseline measurement. An unstructured variance covariance matrix will be used. The parameter estimations are based on the assumption of data being missing at random (MAR) and using the method of restrictive maximum likelihood (REML). MMRM will be used for the primary estimand of the non-radiographic continuous endpoints (refer to Section 9.2.3).

[figure not shown]
Linear Extrapolation for Radiographic Data

For radiographic data (i.e., SHS-based endpoints), linear extrapolation will be applied to subjects with missing data including those due to premature discontinuation of study drug or meeting the rescue criteria, where the missing x-ray at the time point of interest will be imputed assuming a linear relationship across visits. Linear extrapolation will be used to facilitate the primary estimand for radiographic endpoints (refer to Section 9.2.3). Linear extrapolation will not be provided for Week 104 analysis and future analyses.

As Observed (AO)

The AO data handling will not impute values for missing evaluations, and thus a subject who does not have an evaluation on a scheduled visit will be excluded from the AO analysis for that visit. Regardless of premature discontinuation of study drug or use of rescue medication, all observed data will be used in the analysis. The AO data handling will be used to facilitate the supplementary analysis for both binary and continuous endpoints including radiographic endpoints (refer to Section 9.2.2 and Section 9.2.3 where the corresponding supplementary estimands for the primary and ranked secondary endpoints are described respectively).

The intention-to-treat (ITT) principle for the analysis using AO data, AO (with imputation), where additional missing data will be imputed as non-responders, will be used for the supplementary analysis of the primary and key secondary binary endpoints. AO with imputation will not be provided for Week 104 analysis and future analyses.

Mixed Effect Model Repeat Measurement (MMRM) and Generalized Linear Mixed Model (GLMM) for Long-Term Analysis

[figure not shown]
The repeated measure analysis will be conducted using mixed model including As Observed measurements at all visits. MMRM will be used for continuous endpoints and GLMM will be used for non-radiographic binary endpoints. The mixed models will include the categorical fixed effects of treatment, visit and treatment-by-visit interaction, and stratification factor current DMARD use (yes/no). The categorical fixed effect of subject's discontinuation status may also be included in the model as appropriate. For the MMRM analysis of change from baseline in continuous endpoints, the baseline measurement will be included as a continuous fixed covariate. Unstructured, Toeplitz, compound symmetry, or other covariance structures may be considered.

9.2 Efficacy Analysis through Week 24

9.2.1 Primary Efficacy Analysis of the Primary Efficacy Endpoint

The primary efficacy endpoint is ACR20 response at Week 12. The primary estimand is the difference in the proportion of PsA patients who achieved ACR20 response at Week 12 and did not discontinue study drug by Week 12, comparing those who are randomized to each upadacitinib dose group and received study drug to those who are randomized to placebo and received study drug.

Analysis of the primary endpoint will be conducted on the FAS based on randomized treatment groups (upadacitinib 15 mg QD, upadacitinib 30 mg QD versus the combined placebo groups). Point estimate and 95% CI using normal approximation will be provided for the response rate for each randomized treatment group. Comparisons of the primary endpoint will be made between each upadacitinib dose and the combined placebo group using the Cochran-Mantel-Haenszel test (CMH) (refer to Appendix A) adjusting for the main stratification factor of current DMARD use (yes/no). Point estimate, 95% CI using normal approximation and p-value for the treatment comparison will be presented. Nominal p-values constructed using the CMH test will be provided. The multiplicity adjusted (as described in Section 9.2.5) testing results (significant or not significant) will

also be provided. NRI data handling will be used to facilitate the primary estimand. In addition, the number and percentage of non-responders by the intercurrent events, such as discontinuation of study drug prior to or at Week 12 or missing Week 12 ACR measurement will be summarized.

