8.1.4.1 Primary Efficacy Variable

Analysis of the primary endpoint will be conducted on the FAS based on treatment as randomized. Comparison of the primary endpoint will be made between each upadacitinib dose group and the combined placebo groups using the Cochran-Mantel-Haenszel test adjusting for main stratification factors. For the primary analysis, Non-

Responder Imputation (NRI) will be used. The analysis will be repeated using Observed Cases (OC). Supportive analysis will also be conducted on the Per Protocol Analysis Set.

The primary efficacy analyses will also be performed in demographic subgroups including age, gender, race, body mass index, and geographical region to assess the consistency of the treatment effect. Additional subgroup analyses based on baseline disease characteristics and stratification factors will also be conducted.

[figure not shown]

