8.1.4.2 Key Secondary Efficacy Variables

Unless otherwise specified, comparisons are between each dose group of upadacitinib and the combined placebo group.

For binary endpoints, frequencies and percentages will be reported for each treatment group. Similar analyses as for the primary endpoint will be conducted.

For ACR20 response rate at Week 12, analysis will be conducted to assess the non-inferiority of each upadacitinib dose versus ADA on placebo-subtracted treatment difference using Koch's 3-arm test statistic. Non-inferiority will be claimed if upadacitinib preserves at least 50% of the placebo-subtracted ADA effect, i.e., the multiplicity adjusted lower confidence limit for the ratio of placebo-subtracted upadacitinib ACR20 rate versus the placebo-subtracted ADA ACR20 rate is at least 50%. Superiority of upadacitinib versus ADA will also be tested for ACR20 at Week 12.

For continuous endpoints, the mean, standard deviation, median, and range will be reported for each treatment group. Pairwise comparisons between each upadacitinib dose group and the combined placebo groups will be carried out using the Mixed-Effects Model Repeated Measures (MMRM) with treatment group, visit, treatment-by-visit interaction as the fixed factor, and the corresponding baseline value and the main stratification factors as the covariates. For change from baseline in Patient's Assessment of Pain NRS and change from baseline in HAQ-DI at Week 12, superiority of upadacitinib vs ADA will also be tested.

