8.1.4.5 Imputation Methods

The following methods will be used for missing data imputation:

Observed Cases (OC): The OC analysis will not impute values for missing evaluations, and thus a subject who does not have an evaluation on a scheduled visit will be excluded from the OC analysis for that visit.

Multiple Imputation (MI): The MI analysis imputes missing data multiple times under appropriate random variation and thus generates multiple imputed "pseudo-complete" datasets. Results will be aggregated across the multiple imputed datasets, overcoming drawbacks of the single imputation methods.

Non-Responder Imputation (NRI): NRI applies to binary endpoints only. In NRI analysis, subjects who prematurely discontinue study drug will be considered non-responders for visits after the discontinuation.

[figure not shown]
Linear Extrapolation for Radiographic Data: For radiographic data (i.e., SHS-based endpoints), if a subject prematurely discontinued before Week 24/56, their Week 24/56 data will be imputed assuming a linear relationship between baseline and the time point when x-ray should be collected.

Mixed Model Repeated Measures (MMRM): The MMRM includes treatment, visit, and treatment-by-visit interaction as fixed effects, and baseline as covariate.

For non-radiographic data, the NRI approach will serve as the primary analysis approach for binary endpoints. Analysis for key binary endpoints will also be repeated using OC. The mixed model repeated measures (MMRM) will serve as the primary analysis for key continuous endpoints at Week 12 which are prior to potential modification of background therapy. The Multiple Imputation (MI) approach will serve as the primary analysis for key continuous endpoints at Week 24. A Missing Not At Random (MNAR) model that varies assumptions for the missing data in active treatment groups and placebo groups may be used as a sensitivity analysis for important continuous endpoints to account for potential deviation from the missing at random assumption. For radiographic data, both linear extrapolation and as-observed analysis will be conducted.

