8.3 Randomization Methods

Subjects will be randomly assigned in a 2:2:2:1:1 ratio to one of the five treatment sequences per study design diagram Figure 1.

Randomization will be stratified by extent of psoriasis (\geq 3% body surface area [BSA] or < 3% BSA), current use of at least 1 DMARD, presence of dactylitis, and presence of enthesitis, except for subjects from China and Japan, where randomization for each country will be stratified by extent of psoriasis (\geq 3% body surface area [BSA] or < 3% BSA) only. See Section 5.5.3 for details.

[figure not shown]

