- Group 2: Upadacitinib 30 mg QD, N = 410 (Day 1 to Week 24) → Upadacitinib 30 mg QD (Week 24 and thereafter)
- Group 3: Adalimumab (40 mg eow) (N = 410)
- Group 4: Placebo, N = 205 (Day 1 to Week 24) → Upadacitinib 15 mg QD (Week 24 and thereafter)
- Group 5: Placebo, N = 205 (Day 1 to Week 24) → Upadacitinib 30 mg QD (Week 24 and thereafter)

Randomization will be stratified by extent of psoriasis (\geq 3% body surface area [BSA] or < 3% BSA), current use of at least 1 DMARD (Yes or No), presence of dactylitis, and presence of enthesitis, except for subjects from China and Japan, for which randomization will be stratified by extent of psoriasis (\geq 3% body surface area [BSA] or < 3% BSA) only. See Section 5.5.3 of protocol for details.

A schematic of the overall study design is shown in Figure 1 below.

Figure 1. Study Design

- a. All subjects will receive x-rays of hands and feet at Screening, Wk 24, Wk 56, Wk 104, Wk152, and Wk 260/PD.
- b. At Week 16 rescue therapy will be offered to subjects classified as non-responders (defined as not achieving at least 20% improvement in either or both tender joint count (TJC) and swollen joint count (SJC) at both Week 12 and Week 16) as described in Protocol Section 5.2.3.4.
- c. At Week 24, all placebo subjects will switch to Upadacitinib 15 mg QD or 30 mg QD (1:1 ratio) regardless of response.

Note: For subjects in Japan only: Upon approval of protocol amendment 6.01, subjects receiving upadacitinib 30 mg QD will be switched to upadacitinib 15 mg QD prior to marketing approval in Japan for the treatment of psoriatic arthritis.

Note: Upon approval of protocol amendment 7 and 7.01, subjects receiving upadacitinib 30 mg QD will be switched to upadacitinib 15 mg QD at their next scheduled study visit in other countries.

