For ACR20 response at Week 12, analysis will be conducted to assess the non-inferiority of each upadacitinib dose versus adalimumab on the placebo-subtracted treatment difference using Koch's 3-arm test statistic as described in Appendix C. The test aims to show that upadacitinib preserves at least 50% of the placebo-subtracted adalimumab effect. If statistical significance is achieved for the non-inferiority assessment, superiority of upadacitinib versus adalimumab will be tested for ACR20 subsequently as described in Section 9.2.5.

Non-Radiographic Continuous Endpoints

For non-radiographic continuous endpoints, the estimand is the difference in mean change from baseline at the protocol defined time point (e.g., HAQ-DI at Week 12) under the assumption that patients with missing data, including those due to premature discontinuation of study drug, can have their measurements at the protocol defined time point predicted by their observed data and the observed data for other patients for their respective assessments during follow-up. The comparison is for each upadacitinib dose group vs placebo for patients randomized and treated with at least one dose of study drug.

To analyze the primary estimand for the continuous ranked secondary efficacy endpoints, statistical inference will be conducted using the MMRM model and the associated data handling as described in Section 9.1.2, with fixed effects of treatment, visit, treatment-by-

[figure not shown]
visit interaction, the stratification factor of current DMARD use (yes/no) and the continuous fixed covariate of baseline measurement. The LS mean and 95% CI for each randomized treatment group and the LS mean treatment difference, the associated 95% CI and the p-value between each upadacitinib dose group and the combined placebo group will be provided. For change from baseline in Patient's Assessment of Pain NRS and change from baseline in HAQ-DI at Week 12, superiority of upadacitinib vs. adalimumab will also be tested using the same MMRM model.

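### Minor: the SAP's efficacy models carry one of the four randomization factors, Appendix A pairs an unstratified interval with a stratified p-value, and Table 7 omits three promised subgroup factors

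*SAP*

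**What the plan says.** **Randomization.** Protocol 8.3 names four factors: BSA at or above versus below 3%, current use of at least one DMARD, dactylitis and enthesitis, "except for subjects from China and Japan, where randomization for each country will be stratified by extent of psoriasis" only. SAP 4.2 agrees ("except for subjects from China and Japan, for which randomization will be stratified by extent of psoriasis"), though it does not say that the two countries are handled separately.

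**Adjustment in the protocol.** Section 8.1.4.1 specifies a "Cochran-Mantel-Haenszel test adjusting for main stratification factors", in the plural and without naming them. Section 8.1.4.2 gives the MMRM "the corresponding baseline value and the main stratification factors as the covariates". Section 8.1.4.5 describes the same model without them: "The MMRM includes treatment, visit, and treatment-by-visit interaction as fixed effects, and baseline as covariate".

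**Adjustment in the SAP.** Section 9.2.1 settles on a CMH test "adjusting for the main stratification factor of current DMARD use (yes/no". The MMRM in 9.2.3 uses "the stratification factor of current DMARD use (yes/no) and the continuous fixed covariate of baseline measurement". Current DMARD use is also the only randomization factor in the ANCOVA and the SHS random-coefficient model (9.2.3), the additional endpoints (9.2.4), the tipping-point ANCOVA (Appendix D) and the long-term MMRM and GLMM (9.1.2). Most of the continuous models add the baseline value. The three-arm non-inferiority statistic in Appendix C uses crude proportions and no stratification factor.

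**Appendix A.** The text attributes the statistics to the Mantel-Haenszel method. The example code takes the risk difference and Wald interval from `TRTP*aval` and only the p-value from `DMARDBL*TRTP*aval`.

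**Subgroups.** Protocol 8.1.4.1 states: "Additional subgroup analyses based on baseline disease characteristics and stratification factors will also be conducted". SAP Table 7 (9.2.6) includes current DMARD use but not BSA, dactylitis or enthesitis.

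**The concern.** Stratified randomization balances the arms on the stratifying factors. Where these predict outcome, the treatment difference varies less from trial to trial than a variance formula that ignores them assumes. Standard errors are then too large, intervals too wide and tests conservative. The plan balances on four factors and uses one of them in the analysis.

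The Appendix A mismatch means that the interval and p-value reported for one comparison answer to different analyses and can disagree near the significance boundary. The Table 7 gap leaves a protocol commitment unmet, and it rests on no modelling assumption.

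**Working it through.** **1. The plan's own power figures.** Inputs (SAP 4.3): 410 per compared group, 10% dropout, so 0.9 × 410 = 369; two-sided 0.025, critical value 2.241.
- ACR20, 30% vs 50%: the null SE is √(2 × 0.4 × 0.6/369) = 0.0361 and the alternative SE is √((0.21 + 0.25)/369) = 0.0353. Power = Φ((0.20 − 2.241 × 0.0361)/0.0353) = Φ(3.375) = 99.96%. Stated: at least 90%.
- SHS, standardized effect 0.26: Φ(0.26/√(2/369) − 2.241) = Φ(1.29) = 90.2%. Stated: approximately 90%.

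Both figures reproduce.

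**2. Binary endpoints, simulated.** The documents give no factor odds ratios, so a common OR of 1, 1.5 or 2 per factor is assumed. The set-up was 20,000 trials per scenario, N = 1640, blocks of 8 (size assumed), placebo groups combined, and a China and Japan share of 10% (assumed). Dactylitis at 33% and enthesitis at 38% are mid-range of the 8–59% and 25–51% in Protocol 3.0. BSA ≥ 3% at 50% and DMARD use at 80% are assumptions. The level is 0.0499/2 (SAP 9.2.5), critical value 2.242. Each trial was analysed by CMH with different strata.

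| Quantity | Strata in CMH | OR 1 | OR 1.5 | OR 2 |
|---|---|---|---|---|
| Type I error (nominal 0.02495) | DMARD | 0.024 | 0.022 | 0.020 |
| | all four | 0.025 | 0.023 | 0.024 |
| Power, 30% vs 40% | DMARD | 78.0 | 78.3 | 78.7 |
| | BSA × DMARD | 78.0 | 78.6 | 79.5 |
| | all four | 77.9 | 79.2 | 81.0 |
| Power, 30% vs 38.5% | DMARD | 62.9 | 63.9 | 63.9 |
| | BSA × DMARD | 63.0 | 64.3 | 64.9 |
| | all four | 62.9 | 64.8 | 66.8 |

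Monte Carlo SE is about 0.001 for type I error and 0.3 points for power. The loss (all four minus DMARD only) is about 0, 0.9 and 2.3 to 2.9 points. If BSA alone is prognostic (OR 2), it is 79.5 − 78.7 = 0.8 points.

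A second simulation used two arms, 738 subjects and prevalences of 0.5, 0.8, 0.3 and 0.6. At a 12-point difference it gave 87.9% vs 88.3% at OR 1.5 and 89.4% vs 91.3% at OR 2.2. At the planned 20 points, both analyses had about 100% power.

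**3. China and Japan.** At OR 2 and 30% vs 40%, a joint share of 0% or 20% gives 79.2% or 79.0% for DMARD only, and 81.5% or 81.1% for all four factors. The share makes no measurable difference.

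**4. Continuous endpoints.** Let the omitted factors explain a fraction R² of residual variance (assumed). Then SD(Z) = √(1 − R²). An analysis with 60% power when fully adjusted has mean Z of 2.242 + 0.253 = 2.495, so unadjusted power is Φ(2.495 − 2.242/√(1 − R²)).
- R² = 2%: SE 1.0% too wide; Φ(2.495 − 2.265) = 59.1%.
- R² = 5%: SE 2.6% too wide; Φ(2.495 − 2.300) = 57.7%.

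**5. Appendix A.** Results for OR 1 / 1.5 / 2:
- Under the null, the crude Wald SE exceeds the empirical SD by 0.3 / 1.9 / 4.2%, and 95% coverage is 95.0 / 95.5 / 95.9%.
- At 30% vs 40%, the crude and DMARD-stratified Mantel-Haenszel differences diverge on average by 0.0003 / 0.0007 / 0.0011.
- There, the crude interval and the CMH p-value disagree at the 5% level in 0.3 / 0.5 / 0.7% of trials.

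**6. Logit scale.** At an assumed 50% vs 60%, adding the three factors moves the conditional treatment odds ratio from 1.504 to 1.521 (factor OR 1.5) or from 1.510 to 1.559 (factor OR 2). The response difference stays at 10 points.

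**The case against.** The strongest reply is that this is a design preference.

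- **Pre-specification.** Protocol 8.1 leaves details to the SAP, and *main* factors can mean a subset. SAP 12.0 records that version 3.0 went to FDA before the Week 24 lock and unblinding. The changes listed in 11.1 do not touch the Week 24 adjustment. This stands: the SAP narrows an open protocol phrase and does not contradict it.
- **Size.** A loss of 2 to 3 points needs an odds ratio of 2 on every factor and an effect well below the planned one. This stands.
- **Sparse cells.** With 820 subjects in a comparison, the smallest four-factor cell is expected to hold 820 × 0.5 × 0.2 × 0.33 × 0.38 ≈ 10, or 820 × 0.5 × 0.2 × 0.08 × 0.25 ≈ 2 at the low prevalences. Some ranked endpoints are already restricted to BSA ≥ 3%, LEI > 0 or LDI > 0. This argues for collapsing strata but does not justify dropping the factors everywhere.
- **Appendix A is example code.** It is cited only within SAP 9.2 (through Week 24), and a Wald interval is the normal approximation that 9.2.1 asks for. The crude difference also estimates the stated estimand. The ranked tests start at 0.0499/2, so a 95% interval was never the decision rule. All fair; but the text names Mantel-Haenszel and the code for the difference does not use it.
- **Long-term comparisons.** A reader might infer from SAP 9.3 that nominal p-values against adalimumab come from the MMRM or GLMM. The text attaches them to the As Observed analysis up to Week 56, leaves later comparisons optional, and promises only per-sequence estimates from the models. Appendix F mentions adalimumab comparisons without tying them to a model. Any gain is therefore precision in comparisons actually made.

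None of this answers the Table 7 omission.

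**Conclusion.** The point holds as a minor one about efficiency and consistency. Omitting prognostic randomization factors costs between nothing and about 3 points of power at a borderline effect. That range rests on assumed odds ratios of 1 to 2 per factor and assumed prevalences. At the planned ACR20 effect the cost is invisible. The Appendix A mismatch is real but numerically small, and the Table 7 omission follows from the text alone.

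Three stronger readings are tempting and unsupported:
- **Bias or inflated type I error.** A reader might infer this from the missing factors. Simulated type I error is at or below nominal, within Monte Carlo error.
- **A flaw specific to China and Japan.** There the only named randomization factor is absent from the models. But three of four are absent elsewhere too, the models pool all countries, and the countries' share has no measurable effect.
- **A need to redo the confirmatory results.** SAP 11.1 says primary and Period 1 reporting are complete under version 3.0. The analysis used is valid, and a post hoc re-run of all ranked endpoints is not needed.

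**What to change.** 1. **Appendix A.** Take the Mantel-Haenszel common risk difference and its interval from the same DMARD-stratified table as the CMH p-value. This is one line of code. It affects the documentation and any later comparison programmed from the example.
2. **Results still to be reported under SAP 4.0** (9.1.2, 9.3, Appendix F). Where MMRM, GLMM or adalimumab comparisons remain, add BSA extent, dactylitis and enthesitis to DMARD use. Omit any factor fixed by the endpoint's sub-population, and collapse to BSA × DMARD where cells are sparse. State that GLMM results are marginal response rates, because the conditional odds ratio shifts as factors are added. This takes a few sentences and uses baseline data already collected.
3. **Table 7.** Add BSA, dactylitis and enthesitis to the primary-endpoint subgroups, as estimates and intervals without p-values, in line with 9.2.6. Since SAP 4.0 covers only future long-term reporting, label them as produced after the Week 24 lock.

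Leave the completed confirmatory results unchanged. The total cost is a few lines of SAP text and code, and some sparse strata to handle.
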